3.2 Initial Escalation

All Initial Escalation doses will be administered by investigational site personnel to the subjects under direct supervision. Eligible subjects will be randomized and receive treatment with IP on Day 1, starting at a dose of 0.5 mg, increasing the dose at 20- to 30-minute intervals to a maximum dose of 6 mg ([Table 1](#)), according to the Schedule of Events (SOE) in [Appendix 1](#). Subjects who fail to tolerate ≥ 3 mg dose on Day 1 will be considered escalation failures and will be discontinued. Subjects who tolerate ≥ 3 mg dose on Day 1 will undergo confirmatory dosing of a single 3 mg dose on the following day, Day 2. Subjects who do not tolerate this confirmatory dose will be discontinued. Subjects who tolerate this confirmatory dose will enter the Up-Dosing Period.

Table 1: Initial Escalation Schedule

Initial Escalation Schedule		
Day 1 Dose Number	Investigational Product Dose, mg ^a	Cumulative Dose, mg
1	0.5	0.5
2	1	1.5
3	1.5	3
4	3	6
5	6	12
Day 2 Dose Number	Investigational Product Dose, mg	Cumulative Dose, mg
1	3	3

^a All mg doses shown refer to milligrams of peanut protein or the equivalent placebo dose.

Doses will be delivered at 20 to 30 minute intervals under direct observation.

Capsules are to be opened, contents sprinkled over an age-appropriate food, and mixed thoroughly and consumed.

Day 1: Subjects who are unable to tolerate at least a single dose of 3 mg at the end of Day 1 will be considered escalation failures. Subjects who tolerate ≥ 3 mg on Day 1 will return on Day 2 to receive a 3 mg single dose.

Day 2: Subjects with either no symptoms or mild symptoms on Day 2 at 3 mg will start daily home-dosing at 3 mg on Day 3.

Subjects with moderate or severe symptoms at 3 mg on either Day 1 or Day 2 will be considered escalation failures and will be discontinued from the study.

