Subjects may drink fluids and eat foods to which they are not allergic during the day of the initial day escalation procedure while they are being given the desensitization doses. At a minimum, subjects must be observed for 1.5 hours after completion of dose escalation, with vital sign measurements and assessment for signs and symptoms of allergic reaction performed every 30 minutes. Any signs or symptoms of allergic reaction will be recorded in the case report form (CRF) on the appropriate Dosing Symptom/AE form.

If Day 1 dose escalation is completed with no symptoms detected after 1.5 hours of post-dose observation, the subject will be able to leave the CRC. If the subject exhibited mild symptoms,

the duration of the observation period should be a minimum of 1 hour after resolution of the symptoms. For moderate symptoms, the observation period should be extended to a minimum of 2 hours after resolution of the symptoms. And for severe symptoms, the subject should be observed for a minimum of 3 hours after resolution of the symptoms, either at the CRC or an emergency facility, as appropriate.

Any subject deemed to have severe symptoms that include hypoxia, hypotension, or change in mental status, stage 3 anaphylaxis defined in [Appendix 4](#), or who receives intensive therapy (to be determined by the Investigator, but may include such interventions as IV epinephrine, intubation, or admission to an intensive care unit) for an allergic reaction at any time should be discussed with the Medical Monitor and discontinued from the study.

If dose-limiting symptoms occur at or before the 3 mg single dose, there will be no further dosing of IP, and the subject will be classified as an escalation failure and a non-responder for the purpose of primary and key secondary analyses. The subject will be asked to return to the CRC 14 days following the last dose of IP to undergo an Early Discontinuation Visit (Section [6.3.6](#)). AEs will be evaluated from the onset until the event is resolved or medically stable, or until 30 days after the Early Discontinuation Visit, whichever comes first.

If no dose-limiting symptoms occur during Day 1 dose escalation, or if dose-limiting symptoms occur only with the 6 mg single dose, the subject is to return to the CRC on Day 2 to confirm the tolerability of a single 3 mg dose of IP.

6.3.2 Initial Escalation: Day 2

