6.5 Assessment and Treatment of Allergic Reactions to Peanut

6.5.1 Definitions of Symptom Severity

Subjects may develop allergic symptoms during the course of OIT, similar to those seen during other desensitization protocols (eg, venom immunotherapy, drug desensitization, desensitization to aeroallergens by subcutaneous injection). The severity of the reaction will be determined on the basis of the Investigator's judgment. The following definitions, developed to be consistent both with the PRACTALL (PRACTical issues in ALLergology Joint United States/European Union Initiative) consensus report and with the CoFAR grading system (table in [Appendix 5](#)) for allergic reactions, are provided as a general guide (Sampson et al, 2012).

Mild symptoms:

- Skin – limited (few) or localized hives, swelling (eg, mild lip edema), skin flushing (eg, few areas of faint erythema), or pruritus (mild, eg, causing occasional scratching)
- Respiratory – rhinorrhea (eg, occasional sniffling or sneezing), nasal congestion, occasional cough, throat discomfort
- Gastrointestinal – mild abdominal discomfort (including mild nausea), minor vomiting (typically a single episode), and/or a single episode of diarrhea

Moderate symptoms:

- Skin – systemic hives (eg, numerous or widespread hives), swelling (eg, significant lip or face edema), pruritus causing protracted scratching, more than a few areas of erythema or pronounced erythema
- Respiratory – throat tightness without hoarseness, persistent cough, wheezing without dyspnea
- Gastrointestinal – persistent moderate abdominal pain/cramping/nausea, more than a single episode of vomiting and/or diarrhea

Severe symptoms:

- Skin – severe generalized urticaria/angioedema/erythema
- Respiratory – laryngeal edema, throat tightness with hoarseness, wheezing with dyspnea, stridor
- Gastrointestinal – severe abdominal pain/cramping/repetitive vomiting and/or diarrhea
- Neurological – change in mental status
- Circulatory – clinically significant hypotension

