Moderate symptoms: For *moderate symptoms*, if the symptoms are not worsening or amassing at a rapid pace, then a stepwise approach to treatment may be taken at the discretion of the Investigator. If the first action undertaken is to implement an observation period, the observation period should not exceed 30 minutes before either the symptoms are noted to be resolving or therapy is instituted. Whether treatment is initiated immediately or after an observation period, the subject may be treated first with antihistamines or immediately with epinephrine, as deemed appropriate by the Investigator. Other therapies may be added either sequentially or simultaneously, per Investigator judgment.

If moderate symptoms occur at any of the doses below 6 mg (ie, up to and including 3 mg), then the desensitization procedure will be discontinued and the subject considered an escalation failure and desensitization non-responder. The decision to discontinue escalation is to be based solely on the determination of whether the allergic reaction was of moderate severity. Although it is generally the case that some form of treatment will be instituted for moderate symptoms, treatment is not a requirement for assessing an allergic reaction as being of moderate severity.

Severe symptoms: For *severe symptoms*, the actions taken should be to discontinue the initial escalation and administer the appropriate rescue medications. The desensitization procedure will be discontinued regardless of the dose at which the severe symptom or symptoms occurred, and the subject will be considered an escalation failure and desensitization non-responder.

The Medical Monitor is available to answer any questions or to assist in any decisions related to the study protocol.

Figure 1: Schematic for Initial Escalation Day 1

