Appendix 4: Criteria for Suspected Diagnosis, and Severity Grading, of Anaphylaxis

Criteria for Suspected Diagnosis

Anaphylaxis is likely when any 1 of the 3 following sets of criteria is fulfilled:

1. Acute onset of an illness (minutes to hours) with involvement of:
 - Skin/mucosal tissue (eg, *generalized* hives, itch or flush, swollen lips/tongue/uvula) *AND*
 - Airway compromise (eg, dyspnea, stridor, wheeze/ bronchospasm, hypoxia, reduced PEFR) *AND/OR*
 - Reduced BP or associated symptoms (eg, hypotonia, syncope, incontinence)
2. Two or more of the following that occur rapidly after exposure to the allergen (minutes to hours):
 - Skin/mucosal tissue (eg, *generalized* hives, itch/flush, swollen lips/tongue/uvula)
 - Airway compromise (eg, dyspnea, stridor, wheeze/bronchospasm, hypoxia, reduced PEFR)
 - Reduced BP or associated symptoms (eg, hypotonia, syncope, incontinence)
 - *Persistent* GI symptoms (eg, nausea, vomiting, crampy abdominal pain)
3. Reduced BP after exposure to the allergen (minutes to hours):
 - Infants and children: low systolic BP (age-specific) or > 30% drop in systolic BP*
 - Adults: systolic BP < 90 mm Hg or > 30% drop from their baseline

* *Low systolic BP for children is defined as < 70 mmHg from 1 month to 1 year; less than (70 mmHg + [2 x age]) from 1 to 10 years; and < 90 mmHg from age 11 to 17 years.*

Note: Isolated skin or mucosal lesions following the ingestion of a food constitute a food-induced allergic reaction.

Criteria for Anaphylaxis Severity Grading

Staging System of Severity of Anaphylaxis	
Stage	Defined by
1. Mild (skin and subcutaneous tissues, GI, and/or mild respiratory)	Flushing, urticaria, periorbital, or facial angioedema; mild dyspnea, wheeze, or upper respiratory symptoms; mild abdominal pain and/or emesis
2. Moderate (mild symptoms + features suggesting moderate respiratory, cardiovascular or GI symptoms)	Marked dysphagia, hoarseness, and/or stridor; shortness of breath, wheezing and retractions; crampy abdominal pain, recurrent vomiting, and/or diarrhea; and/or mild dizziness
3. Severe (hypoxia, hypotension, or neurological compromise)	Cyanosis or SpO ₂ ≤ 92% at any stage; hypotension; confusion; collapse; loss of consciousness; or incontinence

Criteria for diagnosis and for severity grading adapted from [Muraro et al, 2007](#), and [Muraro et al, 2014](#).

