3. Inpatient hospitalization or prolongation of existing hospitalization: The hospital admission should not have been solely for the sake of providing an extended period of observation, as, for example, might be implemented to watch for a delayed or biphasic reaction.
4. Persistent or significant incapacity or substantial disruption of the ability to conduct normal life functions: *No further stipulation.*
5. Congenital abnormality or birth defect: *No further stipulation.*
6. Important medical event that may not result in 1 of the above outcomes, but may jeopardize the health of the study subject or require medical or surgical intervention to prevent 1 of the outcomes listed in the above definition an SAE:
 - *In general, for an anaphylactic episode to be classified as an SAE on the basis of being an important medical event, it should have resulted in an ER visit, and the ER visit should have been associated with intensive therapy. What constitutes intensive therapy is to be determined by the Investigator, but may include such interventions as IV epinephrine, intubation, or admission to an intensive care unit.*
 - *One or 2 intramuscular injections of epinephrine should ordinarily not be construed as intensive therapy.*
 - *If an Investigator assesses an episode of anaphylaxis to be an important medical event when the episode was of mild or moderate severity and did not require intensive therapy, the rationale for the assessment must be explained in detail in the narrative of the event.*

Appendix 7: Exploratory Biochemical and Molecular Sub-study of Peanut-Allergic Children with Oral Immunotherapy-Related Gastrointestinal Symptoms

Background

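### Protocol Sections 3.2 and 6.3.1 send some children to Day 2 dosing after a 6 mg reaction for which Section 6.5.4 stops treatment

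*Protocol*

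**What the plan says.** Day 1 of the initial escalation steps through 0.5, 1, 1.5, 3 and 6 mg. Day 2 is one supervised 3 mg dose.

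- **Protocol 3.2.** A child who tolerates at least 3 mg on Day 1 "will undergo confirmatory dosing of a single 3 mg dose on the following day, Day 2". The severity-based stop is tied to that dose level: "Subjects with moderate or severe symptoms at 3 mg on either Day 1 or Day 2 will be considered escalation failures". Nothing is said about severe symptoms at 6 mg.
- **Protocol 6.3.1.** The Day 1 visit instruction reads "if dose-limiting symptoms occur only with the 6 mg single dose, the subject is to return to the CRC on Day 2". The section also has its own discontinuation list, which begins "Any subject deemed to have severe symptoms that include hypoxia, hypotension, or change in mental status, stage 3 anaphylaxis defined in" Appendix 4 and adds children who receive intensive therapy.
- **Protocol 6.3.2.** A child who tolerates the Day 2 dose starts daily home dosing on Day 3.
- **Protocol 6.5.4, severe symptoms.** "The desensitization procedure will be discontinued regardless of the dose at which the severe symptom or symptoms occurred", and the child is an escalation failure.
- **Protocol 6.5.4, moderate symptoms.** These end the procedure only at doses below 6 mg.
- **Protocol 6.5.4, mild symptoms.** Needing a second medication, or two antihistamine doses, ends the escalation and all further oral immunotherapy. A separate sentence makes epinephrine for dose-related symptoms, however mild, a reason to discontinue the initial escalation.
- **Protocol 4.3.1.** Severe symptoms (CoFAR Grade 3) require termination of study product. This is not confined to cases needing intensive therapy.

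**The concern.** Two mandatory instructions can give opposite answers for the same child. The section that site staff follow on the day tells them to bring the child back. The section on treating reactions tells them to stop.

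What is at stake is subject safety. A child with stridor at 6 mg could be dosed again the next day and be dosing at home the day after that. In up-dosing, Section 6.5.5.1 also allows supervised next-day dosing at a reduced level after a severe reaction, but only after consulting the Medical Monitor. Section 6.3.1 asks for no such consultation for a child outside its list, so the child with the least treatment experience has the weaker safeguard.

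**Working it through.** No plan figure is in dispute, so the check is a side-by-side reading of the rules, followed by a short size calculation.

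**Step 1. Can a severe reaction fall outside the 6.3.1 list?** Yes, under the protocol's own definitions.
- Section 6.5.1 counts as severe respiratory symptoms "laryngeal edema, throat tightness with hoarseness, wheezing with dyspnea, stridor".
- Appendix 4 puts "Marked dysphagia, hoarseness, and/or stridor; shortness of breath, wheezing and retractions" at Stage 2. Stage 3 needs cyanosis or low oxygen saturation, hypotension, or neurological compromise.
- On intensive therapy, Appendix 6 says: "One or 2 intramuscular injections of epinephrine should ordinarily not be construed as intensive therapy". That guidance was written for classifying serious adverse events, but it gives the same examples of intensive therapy as 6.3.1.

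Stridor at 6 mg with stable oxygenation, blood pressure and mental status is therefore severe, yet it is not on the 6.3.1 list.

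**Step 2. Does the 6.5.4 severe rule really reach 6 mg?** The moderate rule already stops escalation at every Day 1 dose below 6 mg. A severe rule that applies at any dose adds a new dose level only at 6 mg, which is where 6.3.1 says to return.

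**Step 3. Is the mild case also in conflict?** Under 6.5.2 a mild reaction may count as tolerated if, among other conditions, it resolves untreated or with one oral antihistamine dose. A child who needed a second medication or two antihistamine doses would be assessed as not tolerating 6 mg. I read that as dose-limiting, so 6.3.1 brings the child back while 6.5.4 ends treatment.

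**Step 4. Outcomes for a child who tolerated 3 mg and then reacted at 6 mg**

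| Reaction at 6 mg | 3.2 and 6.3.1 | 6.5.4 | Conflict |
|---|---|---|---|
| Severe, on the 6.3.1 list | 6.3.1 list discontinues | Discontinue | None between 6.3.1 and 6.5.4 |
| Severe, not on the list | Day 2 dose | Discontinue | Yes |
| Mild, second medication or two antihistamine doses | Day 2 dose | No further treatment | Yes |
| Moderate, no epinephrine | Day 2 dose | Not stopped | No |
| Moderate, epinephrine given | Day 2 dose | Unclear | Open |

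The last row is open because the moderate rule exempts 6 mg, while the epinephrine sentence ends the initial escalation without saying whether that includes Day 2 when 6 mg was the last Day 1 dose.

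**Step 5. Size**
- AR101 subjects, if all 500 are randomized 2:1 and dosed: 500 × 2/3 = 333.
- Section 1.4.1 expects severe symptoms in fewer than about 1% of subjects at some point in dosing: 0.01 × 333 = 3.3, or about 3 children over all dosing.
- Effect on the AR101 percentage discontinuing due to adverse events: 1/333 = 0.3 percentage point per child, and 3/333 = 0.9 point for three. It is nil for a child who then fails Day 2 and is discontinued anyway.
- Whether the child has any treatment-emergent adverse event does not change, because the 6 mg reaction is already one.

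**The case against.** The best defence is that the protocol can be reconciled. Section 6.5.4 is the dedicated section on reactions in initial escalation, its severe rule is unqualified, and mandatory Section 4.3.1 points the same way. Appendix 5 names throat tightness with hoarseness as Grade 3. On that reading, the 6.3.1 sentence about 6 mg was meant for moderate reactions and untreated or lightly treated mild ones, and 3.2 is a design summary that leaves the exception out. A child with stridor who is given epinephrine also meets the separate epinephrine stop in 6.5.4. Figure 1, the Day 1 schematic, is not visible here and may state the rule. Day 2 is one supervised 3 mg dose, active wheezing bars it, and the Medical Monitor can be consulted.

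Much of this stands as evidence of intent: the design is to stop these children. It does not remove the conflict in the text. No order of precedence is stated. Neither 3.2 nor the 6.3.1 sentence refers to 6.5.4, and the narrower list in 6.3.1 could reasonably be taken as complete. The epinephrine stop is in 6.5.4 too, so it adds to what 6.3.1 omits. Nor can a site assume that severe always means stop, since 6.5.2 treats continuation as a decision and 6.5.5.1 allows it in up-dosing. A clear Figure 1 would still disagree with the prose.

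A reader might infer that the 6.5.4 treatment triggers are soft throughout because the paragraph opens with a general qualifier. The text does not support that. The qualifier belongs to the permissive sentence about a single antihistamine dose, and the stopping sentence that follows is unqualified. Only the moderate reaction treated with epinephrine is unclear.

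**Conclusion.** Wrong as written: an internal inconsistency that bears on subject safety. It covers two groups who tolerated 3 mg and reacted at 6 mg: severe reactors outside the 6.3.1 list, and mild reactors who needed a second medication or two antihistamine doses. A moderate reaction alone produces no conflict. One treated with epinephrine is a question for the sponsor, not an error.

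A reader might infer that no more than 3 AR101 children could be affected. The documents do not support a ceiling. The figure below 1% is an approximate expectation from other oral immunotherapy studies over all dosing, it gives no rate at 6 mg, and it does not address the mild group. It suggests that severe cases are few and no more than that.

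A reader might also infer damage to the safety analysis. At 0.3 percentage point per child on discontinuation due to adverse events, the effect is negligible for a handful of children.

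The conclusion assumes that stridor and similar symptoms are graded as in 6.5.1, and that intensive therapy in 6.3.1 means what Appendix 6 says. The second conflict assumes that a mild reaction assessed as not tolerated counts as dose-limiting.

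**What to change.** In 3.2 and 6.3.1, allow Day 2 dosing after dose-limiting symptoms at 6 mg only for a child who had no severe symptom at any Day 1 dose and met no 6.5.4 treatment trigger that bars further treatment. Cross-refer to 6.5.4, and state that all others are discontinued as escalation failures. Add one sentence giving the rule for a moderate 6 mg reaction treated with epinephrine. Check that Figure 1 agrees.

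The cost is about one clause in each of the two sections plus that sentence, by protocol clarification or site letter. No extra data are needed, and the rule in 6.5.4 is kept.

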6.3.3 Up-Dosing (Also Referred to as Build-up) Visits

Up-dosing will last from a minimum of 20 weeks to a maximum of 40 weeks and comprise 10 scheduled up-dosing visits (including the first 300 mg dose of the IP), with the potential for unscheduled visits for assessment of dose tolerability, dose reduction, dose re-escalation, or management of AEs. Subjects reaching this dose will continue in the study for an additional 2 weeks to ensure tolerability of the 300 mg/d dose. If the subject is unable to tolerate the 300 mg dose for the 2-week period, dosing may continue up to a maximum of 48 weeks after Day 1 to ensure tolerability prior to exiting the study.

Subjects will return to the clinic every 2 weeks for up-dosing to a maximum daily dose of 300 mg. The first dose of IP at each new dose level will be administered in the CRC under direct observation and medical supervision.

Subjects must be free from active wheezing, a flare of atopic disease (eg, atopic dermatitis), or suspected inter-current illness prior to any dose escalation. Subjects should be maintained on their current, or a reduced, dose level of IP until their flare of asthma, atopic disease, or inter-current illness has resolved.

Subjects should withhold their daily home dose of IP on in-clinic dosing days, but should take all other prescribed medications as scheduled.

Some or all of the following assessments/procedures will be completed during up-dosing visits in the CRC, according to the SOE:

- Return unused capsules to the clinic
- Monitoring for compliance
- Concomitant medication review
- Limited physical examination
- Diet (food allergen exposure) history update
- Pre-dose vital sign measurement (BP, PR, body temperature)
- PEFR (3 attempts are to be performed). Airflow assessment should as far as possible be measured at the same time at each visit.
- IP administration under observation in the clinic
- Post-dose vital sign measurements (BP, PR) within 15 to 30 minutes post-dose, prior to discharge, and at the Investigator's discretion during the post-dose observation period.
- Optional saliva collection at Week 6 Up-dosing Visit ([Appendix 7](#))
- Monitoring for AEs, including allergic symptoms (Section [7.2](#))
- Completion of the Total Nasal Symptom Score Sheet in subjects with allergic rhinitis ([Appendix 8](#))
- Subjects will be reminded to continue to follow a peanut-avoidant diet for the duration of the study.
- Take home capsules for daily dosing until next visit
- Peanut allergy teaching refresher (as per Section [6.2](#))
- Telephone follow-up call on the day after the visit

At a minimum, subjects must be observed for 1.5 hours after dose administration, with vital sign measurements and assessment for signs and symptoms of allergic reaction performed every 30 minutes. Any signs or symptoms of allergic reaction will be recorded in the CRF on the appropriate Dosing Symptom/AE form.

If up-dosing is completed with no symptoms detected after 1.5 hours of post-dose observation, the subject will be able to leave the CRC. If the subject exhibited mild symptoms, the duration of the observation period should be a minimum of 1 hour after resolution of the symptoms. For moderate symptoms, the observation period should be a minimum of 2 hours after resolution of the symptoms. And for severe symptoms, the subject should be observed for a minimum of 3 hours after resolution of the symptoms, either at the CRC or an emergency facility, as appropriate.

Any subject deemed to have severe symptoms that include hypoxia, hypotension, or change in mental status (stage 3 anaphylaxis defined in [Appendix 4](#)), or who receives intensive therapy (to be determined by the Investigator, but may include such interventions as IV epinephrine, intubation, or admission to an intensive care unit) for an allergic reaction at any time should be discussed with the Medical Monitor and discontinued from the study.

On the day following in-clinic up-dosing, the site is to make telephone contact with the subject's parent/guardian to inquire if any AEs (including allergic symptoms) occurred subsequent to the subject leaving the clinic, and to provide assistance in the recording of any such events in the diary.

A dose escalation attempt may be postponed 1 to 2 weeks if, in the clinical judgment of the Investigator, the current dose level has not been sufficiently well tolerated to proceed to the next dose level. Further, if an Investigator suspects that a subject has not tolerated, or is not tolerating, his or her current dose level, the Investigator should have the subject return to the clinic to determine whether a dose reduction is warranted, and if so, the magnitude of the reduction. Guidelines for setting the new, lower dose are outlined in Section [6.5.5](#) with the dose adjustment depending on the severity of the dose-related symptoms.

Subjects who require dose reduction during a 2-week dosing period will have their escalation schedule reset, as necessary, to maintain the new dose level for a 2-week period prior to attempting to re-escalate.

Following a dose reduction, it is advised that an escalation attempt be made by 4 weeks, unless escalation is to be delayed further due to administration of epinephrine, as defined in Section [5.8](#). Failure to successfully escalate after 3 consecutive attempts, with each attempt spaced \geq 2 weeks apart, will result in the cessation of dosing and the subject being considered an escalation failure and non-responder. The subject will be asked to return to the CRC 14 days following the last dose of IP to undergo an Early Discontinuation Visit (Section [6.3.6](#)) and is to be followed for safety in the interim.

